6.3 Durvalumab BACKGROUND

Durvalumab (MEDI4736) is a human monoclonal antibody (mAb) of the immunoglobulin G (IgG) 1, kappa (IgG1, kappa) subclass that blocks the interaction of PD-L1 (but not programmed cell death - ligand 2 [PD-L2]) with programmed cell death protein 1 (PD 1) on T-cells and cluster of differentiation (CD) 80 proteins on immune cells. Durvalumab is being developed by AstraZeneca/MedImmune for use in the treatment of cancer. (MedImmune is a wholly owned subsidiary of AstraZeneca; AstraZeneca/MedImmune will be referred to as AstraZeneca throughout this document). The proposed mechanism of action for durvalumab is interference in the interaction of PD L1 with PD 1 and CD80. Blockade of PD-L1/PD-1 and PD L1/CD80 interactions releases the inhibition of immune responses, including those that may result in tumor elimination. In vitro studies demonstrated that durvalumab antagonizes the inhibitory effect of PD-L1 on primary human T-cells resulting in the restored proliferation of interferon-gamma ([IFN γ] Stewart et al 2015). In vivo studies have shown that durvalumab inhibits tumor growth in xenograft models via a T cell dependent mechanism (Stewart et al 2015). Based on these data, durvalumab is expected to stimulate the patient's anti-tumor immune response by binding to PD L1 and shifting the balance toward an anti-tumor response. Durvalumab has been engineered to reduce antibody dependent cellular cytotoxicity and complement-dependent cytotoxicity.

To date, durvalumab has been given to more than 6000 patients as part of ongoing studies either as monotherapy or in combination with other anti-cancer agents. Risks with durvalumab include, but are not limited to, diarrhea/colitis, pneumonitis/ILD, endocrinopathies (ie, events of hypophysitis, adrenal insufficiency, hypo- and hyper thyroidism, and type I diabetes mellitus), hepatitis/increases in

transaminases, nephritis/increases in creatinine, pancreatitis/increases in serum amylase and lipase, rash/dermatitis, myocarditis, myositis/polymyositis, other rare or less frequent inflammatory events including neurotoxicities, infusion-related reactions, hypersensitivity reactions, and infections/serious infections.

In monotherapy clinical studies, very commonly AEs reported included events such as fatigue, diarrhea, nausea and vomiting, decreased appetite, and muscle and joint pain. A total of 5% to 10% of patients discontinued the drug due to an AE. Refer to the current version of the IB for a detailed summary of the monotherapy data including AEs, SAEs, and Common Terminology Criteria for Adverse Events (CTCAE) Grade 3 to 5 events reported across the durvalumab program.

The majority of treatment-related AEs were manageable, with dose delays, symptomatic treatment, and in the case of events suspected to have an immune basis, the use of established treatment guidelines for immune-mediated toxicity (see Appendix E).

For information on all identified and potential risks with durvalumab, please refer to the current version of the durvalumab IB.

6.4 mRNA-2416 DOSING RATIONALE

The planned starting dose is 1.0 mg (0.5 mL) of mRNA-2416 on Day 1 and Day 15 of 28-day cycles.

Antibody agonists of OX40 have been tested in Phase 1 trials in cancer patients. Preliminary results demonstrate only low-grade AEs. In a Phase 1 study, the preliminary safety and efficacy of PF04518600 was assessed with doses ranging from 0.01 to 3.0 mg/kg administered IV every 2 weeks. TEAEs were Grades 1 to 2 and were observed in 67.7% of patients; fatigue and decreased appetite were the most common TEAEs (Diab et al 2016). Similar effects were seen in the Phase 1 trial of MOXR0916 (0.2 to 1200 mg IV every 3 weeks) in which only Grade 1 and 2 TEAEs were observed; the most common TEAEs included fatigue, GI symptoms, and infusion reactions.

The dose of mRNA injected may be limited by either local or systemic tolerability or by the maximum volume of mRNA that can be injected. mRNA-2416 has been formulated at 2 mg/mL. Experience with intratumoral injection of the oncolytic viral product talimogene laherparepvec (Imlygic™, T-VEC) suggests that 5 mL is the maximal intratumoral volume per injection. Toxicology studies in non-human primates suggest that a safe starting dose for mRNA-2416, including a 6 times margin of error, is 0.017 mg/kg, or approximately 1 mg in a 70 kg patient.

In the first clinical study of mRNA-2416 it is proposed that the study drug is administered by intratumoral injection on Days 1 and 15 of a 28-day cycle, repeated for a maximum of 6 cycles. The selection of a 14-day dosing regimen is based upon the following:

- The observed pharmacodynamic effects of OX40L may extend to 14 days given that there was an increase in T-cells in tumors 14 days after injection of mRNA encoding murine OX40L (Section 6.2).
- Any local toxicity observed in the GLP toxicology studies after subcutaneous injection of mRNA-2416 was either partially resolved (microscopic changes at the injection site and in the spleen) or fully resolved 14 days after injection (Section 6.2).
- This dosing regimen enables convenient combination in future studies of mRNA-2416 with an anti-PD-1 or anti-programmed death ligand 1 (PD-L1) antibody in accordance with their approved dosing regimens (Planchard et al 2016).

The proposal to repeat administration of mRNA-2416 is justified by the nonclinical efficacy data demonstrating that repeated doses of murine OX40L into tumor-bearing mice are more efficacious than a single administration. Patients who do not experience dose-limiting or other unacceptable toxicity after the first cycle of therapy, and who are otherwise adjudged to benefit from study therapy at the end of Cycle 2 tumor assessment, may continue on study treatment. Repeated dosing for up to 6 cycles (approximately 6 months) is justified on the basis that other immune therapies for cancer, such as PD-1 inhibitors, may not show clinical efficacy immediately. Median time to first response for patients with melanoma treated with the PD-1 inhibitor pembrolizumab was 3 months, with some patients fulfilling the definition of tumor response for the first time after 6 months of therapy ([Robert et al 2016](#)).

All patients in Arm B and patients that are to receive intratumoral injections to visceral lesions will reduce dosing frequency to every 4 weeks after completing 1 cycle of therapy (Day 1 and Day 15 for Cycle 1, then Day 1 only for Cycles 2-6). The choice for this regimen is a balance between the dosing rationale described above and consideration for the clinical feasibility of repeat injections in patients with visceral lesions that require additional utilization of limited institutional resources such as imaging and procedural time by interventional radiology.

6.5 DURVALUMAB DOSING RATIONALE

The planned dose of durvalumab for this study is 1500 mg every 4 weeks (Q4W). A durvalumab dose of 20 mg/kg Q4W is supported by in vitro data, pre-clinical activity, clinical PK/pharmacodynamics, biomarkers, and activity data from Study CD-ON-MEDI4736-1108 (hereafter referred to as Study 1108) in patients with advanced solid tumors and from a Phase I study performed in Japanese patients with advanced solid tumor (Study D4190C00002). A fixed dose of 1500 mg Q4W is supported by results of a population PK analysis.

Pharmacokinetic/Pharmacodynamic data

Based on available PK/pharmacodynamic data from ongoing Study 1108 with doses ranging from 0.1 to 10 mg/kg Q2W or 15 mg/kg every 3 weeks (Q3W), durvalumab exhibited non-linear (dose dependent) PK consistent with target-mediated drug disposition. The PK approached linearity at ≥ 3 mg/kg Q2W, suggesting near complete target saturation (membrane-bound and sPD L1), and further shows that the durvalumab dosing frequency can be adapted to a particular regimen given the linearity seen at doses higher than 3 mg/kg. The expected half-life with doses ≥ 3 mg/kg Q2W is approximately 21 days. A dose-dependent suppression in peripheral sPD-L1 was observed over the dose range studied, consistent with engagement of durvalumab with PD L1. A low level of immunogenicity has been observed. No patients have experienced immune-complex disease following exposure to durvalumab. (For further information on immunogenicity, refer to the current durvalumab IB.)

A population PK model was developed using the data from Study 1108 (doses=0.1 to 10 mg/kg Q2W or 15 mg/kg Q3W; Fairman et al 2014). Multiple simulations indicate that a similar overall exposure is expected following both 10 mg/kg Q2W and 20 mg/kg Q4W regimens, as represented by AUC at steady state (AUC_{ss}) (calculated over 4 weeks). Median C_{max,ss} is expected to be higher with 20 mg/kg Q4W (approximately 1.5-fold) and median C_{trough,ss} is expected to be higher with 10 mg/kg Q2W (approximately 1.25-fold). Clinical activity with the 20 mg/kg Q4W dosing regimen is anticipated to be consistent with 10 mg/kg Q2W and is expected to (a) achieve complete target saturation in majority of patients; (b) account for anticipated variability in PK, pharmacodynamics, and clinical activity in diverse cancer populations; (c) maintain sufficient PK exposure in case of ADA impact; and (d) achieve PK exposure that yielded maximal anti-tumor activity in animal models.

Given the similar area under the serum drug concentration-time curve (AUC) and modest differences in median peak and trough levels at steady state, the observation that both regimens maintain complete sPD L1 suppression at trough, and the available clinical data, the 20 mg/kg Q4W and 10 mg/kg Q2W regimens are expected to have similar efficacy and safety profiles, supporting the use of 20 mg/kg Q4W.

Clinical data

Refer to the current durvalumab IB for a complete summary of clinical information including safety, efficacy, and PK for the 20 mg/kg Q4W regimen.

Rationale for fixed dosing

A population PK model was developed for durvalumab using monotherapy data Study 1108 (N=292; doses = 0.1 to 10 mg/kg Q2W or 15 mg/kg Q3W; solid tumors). Population PK analysis indicated only minor impact of body weight on the PK of durvalumab (coefficient of ≤ 0.5). The impact of body weight-based (10 mg/kg Q2W) and fixed dosing (750 mg Q2W) of durvalumab was evaluated by comparing predicted steady state PK concentrations (5th, median, and 95th percentiles) using the population PK model. A fixed dose of 750 mg was selected to approximate 10 mg/kg (based on median body weight of ~ 75 kg). A total of 1000 patients were simulated using body weight distribution of 40 to 120 kg. Simulation results demonstrate that body weight-based and fixed dosing regimens yield similar median steady state PK concentrations with slightly less overall between-patient variability with fixed dosing regimen.

A fixed dosing approach is preferred by the prescribing community due to ease of use and reduced dosing errors. Given the expectation of similar PK exposure and variability, AstraZeneca considered it feasible to switch to fixed dosing regimens for durvalumab. Based on an average body weight of 75 kg, a fixed dose of 1500 mg Q4W durvalumab (for a body weight-based dose of 20 mg/kg Q4W) is included in the current study.

6.6 PATIENT POPULATION

The population for Dose Escalation was selected as those patients with locally advanced, recurrent or metastatic incurable solid malignancy or lymphoma that has progressed after standard therapy or for which standard therapy has proven to be ineffective or intolerable or is considered inappropriate and are therefore considered to be appropriate candidates for clinical trials exploring new forms of treatment. In the Dose Expansion periods, patients with ovarian cancer of epithelial origin will be enrolled at the MTD and/or RDE.

6.7 STATEMENT OF COMPLIANCE

This study will be conducted in compliance with the protocol, Good Clinical Practice (GCP), and applicable regulatory and Institutional Review Board (IRB)/Independent Ethics Committee (IEC) requirements.

7 STUDY OBJECTIVES AND ENDPOINTS

7.1 PRIMARY OBJECTIVES

The primary objectives of the study are as follows:

Phase 1

- To determine safety and tolerability of escalating intratumoral doses of mRNA-2416 alone and in combination with durvalumab in patients with relapsed/refractory solid tumor malignancies or lymphoma
- To define the maximum tolerated dose (MTD) and recommended dose for expansion (RDE) and schedule for intratumoral injections of mRNA-2416 alone and in combination with durvalumab in patients with relapsed/refractory solid tumor malignancies or lymphoma

Phase II

- To assess objective response rate of mRNA-2416 alone and in combination with durvalumab in ovarian cancer based on Response Evaluation Criteria in Solid Tumors (RECIST) v1.1

7.2 PRIMARY ENDPOINTS

The primary endpoints of the study are as follows:

Phase 1

- Incidence and nature of dose-limiting toxicities (DLTs) with mRNA-2416 alone and in combination with durvalumab
- Incidence, nature, and severity of AEs/serious adverse events (SAEs), graded according to the National Cancer Institute (NCI) Common Terminology Criteria for Adverse Events (CTCAE) Version 4.03 for mRNA-2416 alone and in combination with durvalumab

Phase II

- Assessment of objective response rate of mRNA-2416 alone and in combination with durvalumab in patients with ovarian cancer based on RECIST v1.1

7.3 SECONDARY OBJECTIVES

The secondary objectives of the study are as follows:

- To assess emergence of antibodies against the drug product as well as OX40L, the protein translated by the drug product
- To assess mRNA pharmacokinetics (PK) alone and in combination with durvalumab
- To assess anti-tumor effects of mRNA-2416 alone and in combination with durvalumab
- Phase I only: To assess objective response rate and duration of response of mRNA-2416 monotherapy based on Response Evaluation Criteria in Solid Tumors (RECIST) v1.1 / or Cheson 2014 criteria (lymphomas)

- Phase II only: To assess disease control rate and duration of response of mRNA-2416 alone and in combination with durvalumab based on Response Evaluation Criteria in Solid Tumors (RECIST) v1.1

7.4 SECONDARY ENDPOINTS

The secondary endpoints of the study are as follows:

- Presence and/or concentration of antibodies against the drug product as well as OX40L, the protein translated by the drug product
- Phase I only: Assessment of objective response rate and duration of response (progression-free survival) of mRNA-2416 monotherapy based on RECIST v1.1 or Cheson 2014 criteria (lymphomas); See [Appendix C](#) and [Appendix D](#)
- Phase II only: Assessment of disease control rate and duration of response of mRNA-2416 alone and in combination with durvalumab in patients with ovarian cancer based on Response Evaluation Criteria in Solid Tumors (RECIST) v1.1
- PK parameters for mRNA-2416 alone and in combination with durvalumab: maximum observed concentration (Cmax) and area under the concentration-time curve (AUC)

7.5 EXPLORATORY OBJECTIVES

The exploratory objectives of the study are as follows:

- To assess objective response rate of mRNA-2416 alone and in combination with durvalumab based on Immune-related Response Criteria (irRC) or lymphoma response to immunomodulatory therapy criteria (LYRIC)
- To assess the correlation of other investigational serum-based proteins (eg, anti-drug antibodies) with PK, efficacy, and safety endpoints
- To assess biomarkers of immunological response in tumor and blood of mRNA-2416 alone and in combination with durvalumab.
- To assess pharmacokinetics (PK) of durvalumab in combination with mRNA-2416.

7.6 EXPLORATORY ENDPOINTS

The exploratory endpoints of the study are as follows:

- Assessment of objective response rate of mRNA-2416 alone and in combination with durvalumab based on irRC or LYRIC
- Assessment of the correlation of other investigational serum-based proteins (eg, anti-drug antibodies) with PK, efficacy, and safety
- Evaluation of plasma will include assessment of pro-inflammatory cytokines and interferons
- Evaluations of tumor tissue will include:
 - Expression of OX40 and OX40L and change in expression over the treatment period
 - Expression of other immune-related markers, including PD-1 and PD-L1
 - Infiltration of tumor with immune effector cells, including T cells

- PK parameters for durvalumab in combination with mRNA-2416: maximum observed concentration and area under the concentration-time curve

The on-treatment biopsy timing may be adjusted based on emerging data.

Where possible, outcome measures will be correlated with clinical characteristics such as tumor histotype, dose of mRNA administered, and clinical outcomes.

7.7 SAFETY PARAMETERS

The parameters that will be used to assess safety in this study include the following:

- AEs
- Hematology, clinical chemistry, and liver function tests
- 12-Lead electrocardiogram (ECG)
- Physical examination
- Vital signs and body weight
- Concomitant medications/procedures
- Eastern Cooperative Oncology Group (ECOG) performance status
- Antibodies against OX40L, the protein translated by the drug product, will be reviewed with investigators as data are available.

Where applicable, AEs will be classified according to the NCI CTCAE Version 4.03.

8 STUDY DESIGN

8.1 NUMBER OF PATIENTS

The planned study enrollment is approximately 117 patients. Approximately 57 patients will be enrolled in the Dose Escalation and Dose Confirmation Periods of the study. During the Expansion Period of the study, approximately 60 patients will be enrolled at the MTD/RDE.

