Planned Number of Patients	The planned study enrollment is approximately 117 patients. Approximately 57 patients will be enrolled during the Dose Escalation and Dose Confirmation Periods of the study. During the Expansion Period of the study, approximately 60 patients will be enrolled at the maximum tolerated dose/recommended dose for expansion (MTD/RDE).
Planned Number of Sites	Approximately 15 sites in the United States

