8.2 STUDY DESIGN

This is an open-label, multicenter, Phase I/II Dose Escalation study of repeated intratumoral injections of mRNA-2416 alone (Arm A) and in combination with intravenously administered durvalumab (Arm B) in patients with advanced relapsed/refractory solid tumor malignancies or lymphoma, followed by Expansion periods in patients with ovarian cancer in each treatment arm. The study includes the following 2 treatment arms:

- Arm A: mRNA-2416 alone
- Arm B: mRNA-2416 in combination with durvalumab (PD-L1 inhibitor)

Each arm of the study consists of a Dose Escalation and Dose Confirmation part followed by a Dose Expansion part in ovarian cancer. Each dose level in the Dose Escalation period will be conducted using a standard 3+3 study design in order to determine the safety and tolerability of each dose. For Arm A Dose Escalation, once a dose level has been cleared for safety, that dose level is open to enrollment of up to 9 additional patients who are willing and eligible to undergo tumor biopsy.

Once the expected MTD/RDE has been cleared in Dose Escalation for Arm A, Dose Escalation in Arm B will begin with a dose of 4mg mRNA-2416, 1 dose level lower than the Arm A MTD/RDE according to [Table 1](#).

For both Arms, once the expected MTD/RDE has been cleared in Dose Escalation, Dose Confirmation of the MTD/RDE will be conducted in at least 3 patients with visceral lesions injectable with ultrasound or CT guidance. The purpose of the Dose Confirmation part is to confirm that the dose level determined for patients with accessible lesions is also appropriate for patients with visceral lesions. Dose Confirmation will be conducted in the same fashion as Dose Escalation, as described in Section 8.2.1 and Section 8.4.

For both Arms, once the MTD and/or RDE has been determined in Dose Escalation/Confirmation, patients will be enrolled in an Expansion cohort in order to assess the preliminary anti-tumor activity of mRNA-2416 in ovarian cancer of epithelial origin

The Dose Expansion will consist of 2 investigational groups across the treatment arms summarized as follows and shown in [Figure 1](#):

Arm A: mRNA-2416 alone

[figure not shown]
- Group 1: Ovarian cancer

Arm B: mRNA-2416 in combination with durvalumab

- Group 2: Ovarian cancer

The study schema is presented in [Figure 1](#).

Figure 1: mRNA-2416-P101 Study Schema

1 - Dose Escalation: 3+3 model. DLT window = 1 cycle (28D)

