13.2 SAMPLE SIZE CONSIDERATIONS

No formal sample-size estimation will be performed. The choice of the number of patients will be based on a standard, Phase 1, 3+3 dose escalation design in which 3 to 6 patients are enrolled into each dose cohort.

For the Arm A dose expansion period, the sample size estimation is based on Simon's minimax two-stage design (Richard S, 1989). The null hypothesis that the true overall response rate is 0.05 will be tested, and this design with the sample size of 13 and 14 for the first and second stage, respectively, will provide an overall one-sided alpha value of 0.05 and statistical power of 0.80 when the true overall response rate is 0.20. If there is 1 or more response observed from the 13 subjects in first stage, the study will proceed to the second stage. To account for potential patient drop-out, a total of approximately 30 patients will be enrolled in order to obtain evaluable data from 27 patients. If four or more responses are observed in the 27 evaluable patients, mRNA-2416 will be considered active in ovarian cancer patients, and may warrant further development.

For the Arm B dose expansion period, the sample size estimation is based on Simon's two-stage design (Richard S, 1989). The null hypothesis that the true overall response rate is 0.1 will be tested, and this design with the sample size of 15 and 26 for the first and second stage, respectively, will provide an overall one-sided alpha value of 0.05 and statistical power of 0.80 when the true overall response rate is 0.25. If there is 2 or more responses observed from the 15 patients in first stage, the study will proceed to the second stage. To account for potential patient drop-out, a total of approximately 45 patients will be enrolled in order to obtain evaluable data from 41 patients. If eight or more responses are observed in the 41 evaluable patients, mRNA-2416 in combination with durvalumab will be considered active in ovarian cancer patients, and may warrant further development.

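### The stated expansion size of about 60 (117 overall) is too small for the two Simon designs, which together need up to about 75 enrolled and 68 evaluable patients

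*Protocol*

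**What the plan says.** The headline numbers are in Protocol 2 (Tabulated Protocol Summary), Protocol 8.1 and SAP 4.1. The summary says "The planned study enrollment is approximately 117 patients". Protocol 8.1 divides this in two: "Approximately 57 patients will be enrolled in the Dose Escalation and Dose Confirmation Periods of the study", and "During the Expansion Period of the study, approximately 60 patients will be enrolled at the MTD/RDE". So 57 + 60 = 117.

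Protocol 8.2 says "The Dose Expansion will consist of 2 investigational groups across the treatment arms". There is one ovarian cancer group per arm, so the expansion total is the sum of the two arms.

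Protocol 13.2 sizes each arm by a Simon two-stage design. For Arm A, "The null hypothesis that the true overall response rate is 0.05 will be tested", and 13 + 14 patients "will provide an overall one-sided alpha value of 0.05 and statistical power of 0.80 when the true overall response rate is 0.20". Allowing for drop-out, "a total of approximately 30 patients will be enrolled in order to obtain evaluable data from 27 patients". Arm B tests 0.10 against 0.25 with 15 + 26 patients at the same alpha and power, and "a total of approximately 45 patients will be enrolled in order to obtain evaluable data from 41 patients". SAP 4.1 gives these arm sizes and the 60 and 117 in the same section, without linking them.

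Protocol 8.2.5 and 8.2.6 make the second stage conditional on at least 1 response in 13 (Arm A) or at least 2 in 15 (Arm B). They also let an arm stop short of its first-stage size if enrolment is not feasible.

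**The concern.** The two arm sizes add to 75, not 60. The gap is not a matter of drop-out allowance, because 60 is also below the 68 evaluable patients that the completed designs use.

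Objective response rate in each arm is the Phase II primary endpoint, and 80% power is claimed for each. That power depends on the second stage being available whenever the first stage is passed. If enrolment is managed to the headline total and both arms pass stage 1, the total is reached before both designs are complete, and at least one arm cannot have its stated power. A planned total is also ordinarily the number used for ethics review, site planning and drug supply, so understating it has practical consequences.

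**Working it through.** **Inputs** (Protocol 13.2 and 8.1)

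| | Arm A | Arm B |
|---|---|---|
| Null / alternative response rate | 0.05 / 0.20 | 0.10 / 0.25 |
| Stage 1 size; continue if | 13; at least 1 | 15; at least 2 |
| Total evaluable; active if | 27; at least 4 | 41; at least 8 |
| Enrolled | about 30 | about 45 |

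**1. Do the Simon designs reproduce?** For stage 1 size n1, continuation threshold r1, total n and success threshold r,

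P(success | p) = Σ from x = r1 to n1 of P[Bin(n1, p) = x] × P[Bin(n − n1, p) ≥ r − x].

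- Arm A: alpha 0.042, power 0.801.
- Arm B: alpha 0.043, power 0.803.

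Both meet one-sided 0.05 and 80% power.

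**2. Do the enrolled sizes reproduce?** 1 − 27/30 = 10% drop-out in Arm A and 1 − 41/45 = 8.9% in Arm B. The two allowances are similar, so 30 and 45 follow from 27 and 41.

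**3. Does 60 reproduce?** It does not.

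- Enrolled: 30 + 45 = 75. Shortfall 75 − 60 = 15, and 15/75 = 20%.
- Evaluable: 27 + 41 = 68. Shortfall 68 − 60 = 8 with no drop-out at all.
- Study total: 57 + 75 = 132, against 117.

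**4. Could any split of 60 give 80% power in both arms?** The smallest two-stage designs meeting alpha 0.05 and power 0.80 need 27 evaluable (Arm A) and 40 (Arm B). Since 27 + 40 = 67 exceeds 60, no split works.

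**5. How often are both second stages needed?**

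- Arm A at 0.20: 1 − 0.80^13 = 0.945.
- Arm B at 0.25: 1 − 0.75^15 − 15 × 0.25 × 0.75^14 = 0.920.
- Both: 0.945 × 0.920 = 0.87.
- Both nulls true: 0.487 × 0.451 = 0.22.
- One null and one alternative true: 0.487 × 0.920 = 0.45, or 0.945 × 0.451 = 0.43.

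**6. Power if 60 is enforced and both arms continue.** Stage 1 is as planned. The re-derived cut-off is the lowest that keeps alpha at or below 0.05.

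| Evaluable out of 60 enrolled | Arm completed | Other arm | Power, stated cut-off | Power, re-derived cut-off |
|---|---|---|---|---|
| 54 (10% drop-out) | A, 27 | B, 27 | 0.356 (≥8) | 0.690 (≥6, alpha 0.045) |
| 54 (10% drop-out) | B, 41 | A, 13 | 0.253 (≥4) | 0.498 (≥3, alpha 0.025) |
| 60 (no drop-out) | A, 27 | B, 33 | 0.596 (≥8) | 0.733 (≥7, alpha 0.039) |
| 60 (no drop-out) | B, 41 | A, 19 | 0.544 (≥4) | 0.544 (≥4, alpha 0.013) |

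**7. Expected enrolment**, scaling expected evaluable patients by 30/27 (Arm A) and 45/41 (Arm B):

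- both alternatives true: 26.23 × 30/27 + 38.92 × 45/41 = about 72;
- both nulls true: 19.81 × 30/27 + 26.72 × 45/41 = about 51;
- one of each: about 58 or 65.

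**The case against.** The strongest reply is that 60 is a planning figure and not a limit. The text calls it planned and approximate, and no section tells anyone to close an arm when expansion reaches 60. Each arm has its own size and stopping rule, and no analysis, cut-off or analysis set uses 60 or 117. An arm run to Protocol 13.2 keeps its 80% power. Moreover, 75 and 68 are maxima. A two-stage trial may be budgeted at an expected size, and 60 lies within the 51 to 72 range in step 7. If Arm A stops at stage 1 and Arm B completes, enrolment is 13 × 30/27 + 45 = about 59. The protocol's own background, which reports minimal single-agent activity for OX40 agonists, makes that plausible.

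Much of this stands. The Simon designs are sound, the power losses in step 6 apply only if 60 binds, and 0.87 is the probability when both drugs work, not in every case. But the reply does not reconcile the documents. Neither states an early-stopping assumption, a split of 60 between the arms, or what happens if both continue. The word approximately is attached equally to 30 and 45, and it cannot cover a 25% gap (75/60 = 1.25) or a figure below the evaluable count. If 60 is not a limit, the total is still understated for the case the designs are powered to detect.

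**Conclusion.** The concern holds. The expansion size of about 60 and the total of about 117 do not agree with the arm sizes stated in the same plan, which come to as many as 75 in expansion and 132 overall. The error is in the headline figures and not in the two-stage designs, which reproduce.

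The 15-patient gap is plain addition and needs no assumption beyond both arms proceeding to stage 2. That happens with probability 0.87 under both alternatives and 0.22 under both nulls. The power consequence rests on two further assumptions: that 60 is enforced, and how the places are shared. With Arm A completed and 10% drop-out, Arm B's power falls from 80% to 36% under its stated rule, or to 69% with a re-derived cut-off. With no drop-out the figures are 60% and 73%. No split of 60 gives 80% in both arms.

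**What to change.** In Protocol 2, Protocol 8.1 and SAP 4.1, state expansion enrolment as up to approximately 75 (30 in Arm A, 45 in Arm B) if both arms proceed to stage 2, and study enrolment as up to approximately 132. The word up to matters, since these are maxima.

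If 60 is a real limit, say so instead. State the assumption behind it (one arm stopping at stage 1), say what happens if both arms qualify for stage 2, and give Arm B's power and decision rule for the size it would then have.

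The edit is two numbers in three places. The arm sizes, stage rules and cut-offs in Protocol 13.2 stay as they are. Raising planned enrolment by 15 is a protocol change, so it would go through the usual amendment and IRB review.
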